5.10.5.1. Lipid Measures

Triglycerides, total cholesterol, LDL-C, and HDL-C (results from fasting samples) will take log-transformation before being analyzed by MMRM model defined above for the Safety Population. The last nonmissing measurements will also be log-transformed and analyzed by the previously defined ANCOVA model.

A listing of patients with postbaseline fasting triglyceride value ≥ 400 mg/dL or non-fasting triglycerides > 600 will be provided (scheduled visits, unscheduled visits, and repeat measurements will be included).

5.10.5.2. Liver Enzyme Elevation Measures

The liver enzymes and biomarkers (alanine aminotransferase [ALT], aspartate aminotransferase [AST], Alkaline phosphatase [ALP], total bilirubin [TBL] and Gamma glutamyl transferase [GGT]) will take log-transformation before performing the MMRM and ANCOVA analyses. In addition, the percentage of patients with the following elevations in liver enzymes at any postbaseline visit after randomization including the treatment period and post-treatment follow-up period will be summarized for subsets based on baseline categories.

- The analysis of any postbaseline ALT (AST) ≥ 3 fold (3X) ULN will contain 4 baseline subsets:
 - patients whose non-missing maximum baseline value is less than or equal to 1X ULN,
 - patients whose maximum baseline is greater than 1X ULN but less than 3X ULN,
 - patients whose maximum baseline value is greater than or equal 3X ULN, and
 - patients whose baseline values are missing.
- The analysis of any postbaseline ALT (AST) ≥ 5 X ULN will be contain 5 baseline subsets:
 - patients whose non-missing maximum baseline value is less than or equal to 1X ULN,

- patients whose maximum baseline is greater than 1X ULN but less than 3X ULN,
 - patients whose maximum baseline is greater than or equal to 3X ULN but less than 5X ULN,
 - patients whose maximum baseline value is greater than or equal to 5X ULN, and
 - patients whose baseline values are missing.
- The analysis of any postbaseline ALT (AST) $\geq 10X$ ULN will contain 6 baseline subsets:
 - patients whose non-missing maximum baseline value is less than or equal to 1X ULN,
 - patients whose maximum baseline is greater than 1X ULN but less than 3X ULN,
 - patients whose maximum baseline is greater than or equal to 3X ULN but less than 5X ULN,
 - patients whose maximum baseline is greater than or equal to 5X ULN but less than 10X ULN,
 - patients whose maximum baseline value is greater than or equal to 10X ULN, and
 - patients whose baseline values are missing.
 - The analysis of any postbaseline total bilirubin $\geq 2X$ ULN will contain 4 baseline subsets:
 - patients whose non-missing maximum baseline value is less than or equal to 1X ULN,
 - patients whose maximum baseline is greater than 1X ULN but less than 2X ULN,
 - patients whose maximum baseline value is greater than or equal to 2X ULN, and
 - patients whose baseline values are missing.
 - The analysis of any postbaseline ALP $\geq 2X$ ULN will contain 4 baseline subsets the same as above for total bilirubin

For the above elevation analysis, maximum baseline and maximum postbaseline will be used. Maximum baseline is defined as the maximum non-missing observation in the baseline period. The maximum postbaseline is defined as the maximum non-missing postbaseline measurements including scheduled, unscheduled and retest measurements.

A listing of patients with any post randomization

- elevation of serum ALT to ≥ 5 -fold ULN on 2 or more consecutive blood tests

- elevated serum TBL to ≥ 2 -fold ULN (except for cases of known Gilbert's syndrome)
- elevation of serum ALP to ≥ 2 -fold ULN on 2 or more consecutive blood tests
- study participant discontinued from treatment due to a hepatic event
- hepatic event considered to be an SAE

will be provided, including demographics, disposition, study drug exposure, AEs, concomitant medications, all the liver measurements (ALT, AST, total bilirubin, ALP and GGT). The time course plot of ALT, AST, ALP, TBL and GGT will also be provided for the patients meeting the above criteria.

5.10.6. Electrocardiograms

Electrocardiograms will be collected at specific study visits. For Visit 3, 6, 9, 15 and 17, a triplicate ECG will be collected. The other visits, a single ECG will be collected. The average values will be used in the analysis.

The actual and change from baseline for selected ECG parameters (heart rate and intervals) will be analyzed using the MMRM model. The MMRM model will be used for the analysis during the treatment period and will contain the term for treatment, baseline value, visit, and visit-by-treatment interaction as factors, patient as random effect, and compound symmetric as the variance-covariance structure. The last nonmissing measurements will also be analyzed by the ANCOVA model with treatment and baseline value as covariates.

5.10.7. Immunogenicity

The sample to determine antibody against LY3209590 will be collected at protocol-specified visits. Treatment emergent anti-drug antibodies (TEADA) can be subclassified as either treatment induced (baseline antibody level is not detected) or treatment boosted (baseline antibody level is detected):

- treatment induced response: a postbaseline titer ≥ 2 -fold the minimum required dilution (1:20) if the baseline status is not detected (i.e., titer less than the minimum required dilution)
- treatment boosted response: a postbaseline titer ≥ 4 -fold of the baseline titer if the baseline status is detected. For an example, 1:20 at baseline and 1:80 post baseline is treatment boosted.

The frequency and percentage of a participant's baseline ADA status for patients with baseline and at least one postbaseline measurement, allowing TEADA evaluation, will be summarized.

The TEADA status will be determined by all postbaseline data. The number and percentage of patients with positive TEADA response any time after randomization including the treatment period and follow-up period will be summarized by treatment group.

A listing of anti-LY3209590 antibodies at each visit will be provided for the Safety Population. The listing will include anti-LY3209590 antibody status (detected/not detected), the titer for detected samples and the TEADA status.

5.11. FGM Analysis

5.11.1. General Consideration

The FGM system will be offered to all participants meeting study entry criteria except for reporting of screening clinical laboratory assessments in Study I8H-MC-BDCL (BDCL). Participants will undergo 3 FGM sessions using the LibrePro System (Abbott) in the 14-day period prior to randomization, Visit 15, and Visit 20. Patients will remain blinded to these assessments until the study is completed.

All patients who are randomized to either LY3209590 Algorithm 1 or insulin degludec receive at least 1 dose of study treatment, and have FGM data from baseline and at least 1 postbaseline collection period will be included in the analyses. The data collected after permanent discontinuation of the IP will be censored. There will be no multiplicity adjustment. Additional analysis may be conducted to compare between the LY3209590 (by pooling LY3209590 Algorithm 1 and LY3209590 Algorithm 2) and insulin degludec if deemed necessary.

According to the 2020 American Diabetes Association standard of medical care in diabetes, the FGM data will be included in the analysis only if at least 70% of the total measures in the analysis period are obtained (defined as a valid FGM period). For example, the 24-hour period will have 96 measures and the minimum number of measures will be 68. All the FGM derivations are based on the data from valid FGM period unless otherwise specified.

The FGM variables will be derived for each FGM day when the analysis data meeting the above requirement. The derived variables for a visit will be based on the daily FGM variables within the given visit.

Summary statistics will include the number of observations, mean, median, maximum, minimum, and SD for all continuous measures. For categorical measures, the number of observations, proportion, and frequency will be included in summary statistics. All analyses will be performed by visit and treatment.

5.11.2. FGM Variable and Analysis

The continuous variables derived from FGM will be summarized and compared between treatment groups by visit using MMRM model. The model will include the treatment, HbA1c stratum (<8.5% or ≥8.5%), baseline value of the dependent variable, visit, and treatment by visit interaction. The raw mean and LS mean difference between treatment groups will be summarized.

For the between-day and within-day glucose variability, the variable will take log-transformation before performing the MMRM analysis.

The binary variables will be analyzed using a longitudinal logistic regression. In the longitudinal logistic regression model, the independent variables of treatment, baseline HbA1c value, baseline continuous variable corresponding to the binary dependent variable, visit, and treatment by visit interaction will be used.

For the hypoglycemia episodes defined by FGM, the analysis using a negative binomial model with the offset of log (exposure in year) will be performed. The model will include treatment and baseline HbA1c.

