6.3. Measures to Minimize Bias: Randomization and Blinding

This is an open-label study; thus, it will be unblinded. However, the specific intervention to be taken by a participant will be assigned using an interactive web–response system (IWRS). The site will contact the IWRS prior to the start of study intervention administration for each participant. The site will record the intervention assignment in the appropriate data capture tool. Potential bias will be reduced by the following steps: central randomization, stratification, blinded adjudication for CV endpoints.

Patients who meet all criteria for enrollment will be randomized to treatment at Visit 3. Assignment to treatment groups will be determined by a computer-generated random sequence using the IWRS. The IWRS will be used to assign IP to each patient. Site personnel will confirm that they have located the correct IP by entering a confirmation number found on the IP label into the IWRS.

To achieve between-group comparability for site factor, the randomization will be stratified by baseline HbA1c (<8.5%, ≥8.5%), DPPIV (yes/no), SGLT2 (yes/no), country, and baseline BMI (<30, ≥30). The randomization scheme will be performed using IWRS, which will ensure balance between treatment groups.

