5.10.4. Vital Signs and Body Weight

Vital signs and weight will be summarized by treatment group and visit. Change from baseline (last nonmissing value up to Visit 3) to postbaseline value for vital signs and weight will be summarized by treatment group and visit for patients who have both a baseline and at least 1 postbaseline result.

Treatment differences in mean change will be assessed using MMRM. The MMRM model will be used for the analysis during the treatment period and will contain the terms for treatment, baseline value, visit, and visit-by-treatment interaction as factors; patient as random effect; and CS as the variance-covariance structure. Only scheduled measures will be included in the MMRM analyses.

An analysis of covariance (ANCOVA) will also be conducted for the last nonmissing values during the study including the safety follow-up visit for the Safety Population. The ANCOVA model will use treatment, baseline value of the dependent variable as covariates.

The percentages of patients with treatment-emergent high or low vital signs at any time after randomization will be summarized and compared between treatment groups using Fisher's exact test. A treatment-emergent high result is defined as a change from a value less than or equal to the high limit (140 mm Hg for systolic blood pressure, 90 mm Hg for diastolic blood pressure, and 100 bpm for pulse) at baseline to a value greater than the high limit at any time that meets the specified change criteria after randomization. A treatment-emergent low result is defined as a change from a value greater than or equal to the low limit (90 mm Hg for systolic blood pressure, 50 mm Hg for diastolic blood pressure, and 50 bpm for pulse) at baseline to a value less than the low limit at any time that meets the specified change criteria after randomization. Patients with missing baseline measures will be excluded from this analysis unless otherwise specified. Scheduled visits, unscheduled visits, and retest measurements will be included in this analysis. Table BDCL.3 will be used to define the low and high limits and change thresholds.

Table BDCL.3. Categorical Criteria for Abnormal Treatment-Emergent Blood Pressure and Pulse Measurement

Parameter	Low	High
Systolic BP (mm Hg) (Supine or sitting)	≤ 90 and decrease from baseline ≥ 20	≥ 140 and increase from baseline ≥ 20
Diastolic BP (mm Hg) (Supine or sitting)	≤ 50 and decrease from baseline ≥ 10	≥ 90 and increase from baseline ≥ 10

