5.10.5. Laboratory Measures

The data from laboratory testing will be summarized by treatment group and visit. Change from baseline (last nonmissing value up to Visit 3) to postbaseline value for laboratory tests (except for FSG, HbA1c, and Antibody) will be summarized for patients who have both a baseline and at least 1 postbaseline result. Treatment differences in mean change for these laboratory tests will be evaluated using MMRM model. The MMRM model will be used for the analysis during the treatment period and will contain the term for treatment, baseline value, visit, and visit-by-treatment interaction as factors, patient as random effect, and compound symmetric as the variance-covariance structure. Analyses will be provided in both international units (SI) and conventional units (CN). The MMRM analysis will only include lab tests for the scheduled visits specified in the protocol. For some selected laboratory measures, log-transformed value will be used in MMRM when necessary, and the geometric LS means as well as the percentage change from baseline will be reported.

The last nonmissing values during the study including the safety follow-up visit for the Safety Population will also be analyzed by an ANCOVA model. The ANCOVA model will use treatment, baseline value of the dependent variable as covariates. For some selected laboratory measures, log-transformed value will be used in the ANCOVA model.

The percentages of patients with treatment-emergent abnormal laboratory results at any time after randomization (including the treatment period and follow-up period) will be summarized

and compared between treatment groups using Fisher's exact test. A treatment-emergent abnormal result is defined as a change from normal at baseline to abnormal at any time after randomization. Covance reference ranges will generally be used to define the low and high limits. Patients with missing baseline lab measures will be excluded from this analysis unless otherwise specified. Scheduled visits, unscheduled visits, and retest measurements will be included in this analysis.

A lab listing in the Safety Population who had an treatment-emergent abnormal laboratory value during the study will be provided, including the actual measurement, abnormal result, and reference low or high limits.

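### The continuous FGM and safety models omit four or all five randomization strata, so their reported standard errors are too large to the extent that those factors predict outcome

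*SAP*

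**What the plan says.** Protocol 6.3 states that "the randomization will be stratified by baseline HbA1c (<8.5%, ≥8.5%), DPPIV (yes/no), SGLT2 (yes/no), country, and baseline BMI" (<30, ≥30). The continuous models use these five factors as follows.

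| Analysis | Stratification factors in the model |
|---|---|
| Primary HbA1c MMRM (SAP 5.7) | Country, DPPIV, SGLT2 and BMI, with HbA1c as a continuous baseline: all five covered |
| Secondary efficacy MMRMs (SAP 5.8) | The primary model, plus the HbA1c stratum for non-HbA1c measures: all five covered |
| Continuous FGM MMRM (SAP 5.11.2) | HbA1c only: "The model will include the treatment, HbA1c stratum" |
| Vital-sign and weight MMRM (SAP 5.10.4) | None: it "will contain the terms for treatment, baseline value, visit, and visit-by-treatment interaction as factors" |
| Laboratory MMRM (SAP 5.10.5) | None: it "will contain the term for treatment, baseline value, visit, and visit-by-treatment interaction as factors" |
| Laboratory ANCOVA (SAP 5.10.5) | None: "The ANCOVA model will use treatment, baseline value of the dependent variable as covariates" |
| ECG MMRM and ANCOVA (SAP 5.10.6) | None: same structure as the laboratory models |

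The ANCOVA for vital signs and weight likewise carries only treatment and the baseline value. Every model in the table adjusts for the baseline of its own dependent variable. The SAP gives no reason for leaving the strata out of the safety and FGM models.

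**The concern.** Stratified allocation forces the arms to be alike on the chosen factors, so those factors contribute little to the chance difference between arms. A linear model without them still counts their variance as residual noise. It therefore reports a standard error that is too large for the design, and its tests reject less often than their nominal level.

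Conservatism is not a safeguard when the aim is to detect or rule out harm. Protocol 4.2 names weight gain among the effects to be compared with degludec. The synopsis justifies the 26-week duration by the need to exclude a rise in ALT. Weight and liver enzymes are both analysed with the models in question, liver enzymes after log-transformation. Wider intervals than necessary make a difference harder to see and an increase harder to exclude.

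**Working it through.** **1. The plan's own figure.** The only design figure is for the primary endpoint (Protocol 9.2): SD 1.1%, margin 0.4%, true difference 0, 2-sided alpha 0.1, 100 completers per arm.

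- SE = 1.1 × √(2/100) = 0.1556
- Power = Φ(0.4/0.1556 − 1.645) = Φ(0.926) = 0.823 (0.821 with the noncentral t)
- 94 per arm would give 80%; 100/(1 − 0.20) = 125 randomized per arm

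The stated power of more than 80% is reproduced. It is not touched by this point, because the primary model already carries the factors.

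**2. Effect on interval width.** Let R² be the share of residual variance that the omitted factors explain, after the terms already in the model. Apart from degrees of freedom, the ratio of interval widths (strata omitted to strata included) is 1/√(1 − R²). The documents give no R², so a range is assumed.

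| Assumed R² | 1/√(1 − R²) | Interval wider by |
|---|---|---|
| 0% | 1.000 | 0% |
| 1% | 1.005 | 0.5% |
| 5% | 1.026 | 2.6% |
| 10% | 1.054 | 5.4% |
| 20% | 1.118 | 11.8% |

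**3. Is this lost precision or an overstated SE?** A simulation separates the two: single-visit ANCOVA, 100 per arm, blocked stratified allocation, 3,000 runs per setting, nominal 2-sided alpha 0.10. Four countries and the factor prevalences are assumptions.

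| R² | Model | Mean reported SE | Actual SD of estimate | Type I error |
|---|---|---|---|---|
| 0% | Baseline only (safety type) | 0.1421 | 0.1406 | 0.099 |
| 0% | Baseline + HbA1c (FGM type) | 0.1416 | 0.1405 | 0.100 |
| 0% | All strata | 0.1422 | 0.1418 | 0.099 |
| 10% | Baseline only | 0.1425 | 0.1363 | 0.078 |
| 10% | Baseline + HbA1c | 0.1419 | 0.1363 | 0.080 |
| 10% | All strata | 0.1352 | 0.1346 | 0.094 |
| 20% | Baseline only | 0.1427 | 0.1313 | 0.069 |
| 20% | Baseline + HbA1c | 0.1420 | 0.1312 | 0.069 |
| 20% | All strata | 0.1276 | 0.1266 | 0.099 |

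The Monte Carlo standard error of a rejection rate of 0.10 is √(0.10 × 0.90/3,000) = 0.0055.

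At R² = 10% the FGM-type model's reported SE is 5.0% above that of the all-strata model (0.1419/0.1352), but its estimate is only 1.3% more variable (0.1363/0.1346). At 20% the figures are 11.3% (0.1420/0.1276) and 3.6% (0.1312/0.1266). Most of the effect is an overstated SE. At R² = 0 adding the strata gains nothing and costs about 0.4% in SE (0.1422/0.1416).

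**4. Logistic models.** These behave differently. With an assumed omitted covariate of log-odds 1.0 per SD and a true treatment log-odds of 0.6 (1,500 runs), leaving it out gave a smaller SE (0.287 against 0.319), an estimate closer to zero (0.53 against 0.62) and power of 59% against 62%.

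**The case against.** The strongest reply is that the harm is conditional and probably small. Each model already contains the baseline of its outcome. Baseline weight should absorb much of the BMI factor in the weight model. Background oral therapy is stable before screening and continues through treatment, and the first FGM session is recorded on that therapy before randomization (Protocol 4.1.1), so the FGM baseline already reflects much of any DPPIV or SGLT2 effect. Nothing in the documents shows that these factors predict ECG intervals or most laboratory tests. The weight, laboratory and FGM endpoints are exploratory and have no decision rule. All of this stands. It argues for the lower end of the range, but it is not a reason to omit factors the trial randomizes by.

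Four stronger readings are tempting, and the documents do not support them:

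- **The plan throws away precision.** Under blocked stratification the design itself delivers most of the precision; the fault is mainly in the SE that is reported.
- **All safety and FGM intervals are too wide.** The binary FGM model uses "the independent variables of treatment, baseline HbA1c value, baseline continuous variable corresponding to the binary dependent variable", and for FGM hypoglycemia episodes "The model will include treatment and baseline HbA1c". These are logistic and negative binomial models. In the logistic check, omission shrank the SE and attenuated the estimate; no check was made for the negative binomial model. Table BDCL.1 also contains a logistic model, in the safety section, that covers all five factors.
- **The SAP contradicts itself.** Section 5.8 applies its model to the listed secondary efficacy outcomes. Safety has its own population and a pooled LY3209590 group. Different models for different classes of outcome are not a contradiction.
- **The primary conclusion is at risk.** It is not, because the primary model covers all five factors.

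**Conclusion.** The omission is plain in the text: four of five factors in the continuous FGM MMRM, and all five in the continuous vital-sign, weight, laboratory and ECG models. The consequence is a reported SE that is too large, and conservative tests, only to the extent that the omitted factors predict the outcome beyond the baseline value. Intervals would be about 0% to 5.4% wider for an R² of 0% to 10%, and 11.8% wider at 20%.

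This rests on an assumed R² and on allocation that is effectively blocked within strata; Protocol 6.3 says the IWRS ensures balance but does not name the method. The simulation uses a single visit, so exact figures for a repeated-measures model with missing data will differ. This is a low-cost improvement to exploratory analyses, not a threat to the trial's main conclusion.

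**What to change.** In SAP 5.10.4 to 5.10.6, add country (pooled as in SAP 5.1), DPPIV (yes/no), SGLT2 (yes/no), BMI (<30, ≥30) and the HbA1c stratum (<8.5%, ≥8.5%) as fixed factors to the continuous MMRMs and ANCOVAs. In SAP 5.11.2, add the four missing factors to the continuous FGM MMRM. State in advance a rule for pooling or dropping sparse levels. SAP 5.1 now says that no country pooling is needed beyond Puerto Rico with the United States, so that sentence would need an exception.

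The cost is SAP wording and a few degrees of freedom, with no new data. The safety models gain four binary terms plus one fewer than the number of countries; the FGM model gains three plus the same. With four countries (assumed, as the documents give no number) that is 4 + 3 = 7 and 3 + 3 = 6 degrees of freedom, against about 200 completers.

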2.2. Background

LY3209590 was designed as a novel, once-weekly, long-acting insulin receptor agonist that is intended for the treatment of hyperglycemia in study participants with T2DM. A once-weekly insulin receptor agonist has the potential to increase willingness to initiate and improve compliance with an insulin therapy in study participants with T2DM. In real life, only about 25% these study participants reach the target hemoglobin A1c (HbA1c) of 7% (Blonde et al. 2014), and a once-weekly insulin receptor agonist could help to increase this number. The potential downside of such a long-acting insulin receptor agonist could theoretically be a higher risk for hypoglycemic events or a longer duration of such events. In contrast to this theoretical risk the recently launched long-acting insulin degludec has shown a reduced potential to induce hypoglycemia as compared to insulin glargine while its half-life is twice as long as that of insulin glargine (Heise et al. 2012). The current Phase 2 study will therefore evaluate the safety and efficacy of LY3209590 as compared to insulin degludec while very closely monitoring glycemic profiles.

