6.1.2.2. Management of Increased Hypoglycemia Risk

The allowable oral antihyperglycemic medications (OAMs) are non-secretagogues; therefore, clinically relevant increases in the risk of hypoglycemia due to the OAMs are not expected in this trial. To date, effects of LY3209590 on hypoglycemia are not different as compared to other basal insulins. An objective of the study is to assess the risk of hypoglycemia in insulin naïve T2DM patients receiving LY3209590 as compared to insulin degludec.

In this study, increased risk of hypoglycemia is defined as having a single episode of severe hypoglycemia or having more than 1 episode of documented hypoglycemia within a 1-week period at any time during the treatment period. Documented hypoglycemia is defined as any time a participant reports a SMBG ≤ 70 mg/dL (< 3.9 mmol/L) or any investigator confirmed case of severe hypoglycemia.

In cases where a patient experiences hypoglycemia as described above, to confirm the increased risk, the study sites must ensure that the patient has been fully compliant with the assigned therapeutic regimen and also that there is no evidence of other possible causes of hypoglycemia (e.g., omission of meal, unexpected increase in exercise).

Patients fulfilling the definition of increased risk of hypoglycemia should first decrease their dose of IP per the respective dosing algorithm, followed by discontinuation of IP, if needed. If the patient continues to experience hypoglycemic events after the discontinuation of IP, the investigator should discontinue the patient from OAM therapy.

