5.11.2.1. Hypoglycemia

- Percentage and Duration (in minutes) of time per day where glucose values are within a hypoglycemic range (defined as <70 mg/dL [3.9 mmol/L]) during the nighttime period (defined as midnight to 0600 hours), the daytime period (defined as 0600 hours to 2400 hours) and a 24-hour period.
- Percentage and Duration (in minutes) of time per day where glucose values are within a hypoglycemic range (defined as <54 mg/dL [3.0 mmol/L]) during the nighttime period, the daytime and a 24-hour period.
- Percentage and Duration (in minutes) of time per day where glucose values are within a hypoglycemic range (defined as defined as <70 mg/dL [3.9 mmol/L] and ≥ 54 mg/dL [3.0 mmol/L]) during the nighttime period, the daytime period and a 24-hour period.
- Incidence of hypoglycemic episodes (defined as <70 mg/dL [3.9 mmol/L], or <54 mg/dL [3.0 mmol/L] or <70 mg/dL [3.9 mmol/L] and ≥ 54 mg/dL [3.0 mmol/L]) during the nighttime period, the daytime period and a 24-hour period.
- Rate of hypoglycemic episodes (defined as <70 mg/dL [3.9 mmol/L], or <54 mg/dL [3.0 mmol/L] or <70 mg/dL [3.9 mmol/L] and ≥ 54 mg/dL [3.0 mmol/L]) during the nighttime period, the daytime period and a 24-hour period.
- Duration (in minutes) of each individual hypoglycemic episode (defined as <70 mg/dL [3.9 mmol/L], or <54 mg/dL [3.0 mmol/L] or <70 mg/dL [3.9 mmol/L] and ≥ 54 mg/dL [3.0 mmol/L] for at least 30 minutes).

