5.11.3.2. Hypoglycemic Episode

The FGM-determined hypoglycemic episode is defined as glucose <54 mg/dL (or ≤ 70 mg/dL) for at least 30 minutes.

The duration of each episode will be calculated using the time difference between the 2 time points before the incidence starts and after the incidence ends.

The average duration will be calculated by dividing the sum of the duration of individual episodes during the given visit by the number of episodes.

The FGM-determined nighttime hypoglycemic episode is defined as hypoglycemic episodes that occur between 2400 hours and 0600 hours. To calculate the duration of nighttime hypoglycemic episode, the end date/time will be the end date/time when the patient passes outside the hypoglycemic range even if it is outside the interval of 2400 hours and 0600 hours.

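### The FGM model for hypoglycemic-episode duration adjusts for a baseline duration that is undefined for patients without a baseline episode, so as written it omits all of them

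*SAP*

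**What the plan says.** SAP section 5.11.2 gives one rule for the whole class: "The continuous variables derived from FGM will be summarized and compared between treatment groups by visit using MMRM model". The model terms are treatment, HbA1c stratum, and "baseline value of the dependent variable, visit, and treatment by visit interaction". The only special handling is a log scale for the glucose-variability measures, which leaves the covariate rule unchanged.

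SAP section 5.11.2.1 lists among the hypoglycemia variables "Duration (in minutes) of each individual hypoglycemic episode". SAP section 5.11.3.2 defines an episode as glucose below the threshold "for at least 30 minutes", and obtains the average duration by "dividing the sum of the duration of individual episodes during the given visit by the number of episodes". No value, indicator or substitute covariate is given for a session without an episode.

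The inclusion rule in SAP section 5.11.1 depends on having sensor data, not on having an episode: dosed patients who "have FGM data from baseline and at least 1 postbaseline collection period will be included in the analyses". The negative binomial model in SAP section 5.11.2, with treatment and baseline HbA1c, covers episode counts and rates but not duration.

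**The concern.** With zero episodes the average is 0/0. A patient whose baseline session has no episode therefore has no covariate value, and a model that needs that value cannot use the patient's later episodes. The patients available to this model are then fewer than the FGM set defined in SAP section 5.11.1, and they are selected for having had low glucose before any study insulin.

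Baseline episodes are likely to be uncommon. The baseline sensor is removed before the first dose (Protocol section 4.1.1). Entry HbA1c is 7.0% to 9.5% (Protocol section 5.1). Sulfonylurea or insulin use in the previous 3 months is excluded, apart from short acute insulin use (Protocol section 5.2). Protocol section 6.1.2.2 adds: "The allowable oral antihyperglycemic medications (OAMs) are non-secretagogues".

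Protocol section 2.2 says the potential downside of such a long-acting product "could theoretically be a higher risk for hypoglycemic events or a longer duration of such events". Minutes per day below range combine how often episodes occur with how long they last. Episode duration is the measure that separates the two, and a null result from a small, selected subset could be misread as reassurance about it.

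**Working it through.** **Plan's own figure.** There is none: the documents give no baseline episode incidence, and no sample size or power for episode duration. Everything numerical below rests on assumed incidences.

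**Inputs (all assumed).** pb = share of patients with a baseline episode, 5-50%. pf = share with a post-baseline episode, 40-80%. OR = odds ratio linking the two, 1-10.

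**Formula.** Let a be the share with an episode in both periods. It solves

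OR = a(1 − pb − pf + a) / [(pb − a)(pf − a)].

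The share of patients with an on-treatment episode that the model loses is 1 − a/pf. Under independence (OR = 1), a = pb × pf and the loss is 1 − pb.

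**Worked cases.**
- pb = 5%, OR = 1: loss = 1 − 0.05 = 95%.
- pb = 20%, pf = 60%, OR = 1: a = 0.20 × 0.60 = 0.12; loss = 1 − 0.12/0.60 = 80%. Of 100 patients in an arm, 12 of the 60 with an on-treatment episode remain.
- pb = 20%, pf = 40%, OR = 10: 9a² − 6.4a + 0.8 = 0, so a ≈ 0.162; loss = 1 − 0.162/0.40 ≈ 60%.
- pb = 40%, pf = 60%, OR = 3: 2a² − 3a + 0.72 = 0, so a = 0.30; loss = 50%.

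**Range over all pf and OR.**

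| Baseline incidence | Loss among patients with an on-treatment episode |
|---|---|
| 5% | 89-95% |
| 10% | 79-90% |
| 20% | 60-80% |
| 30% | 43-70% |
| 40% | 29-60% |
| 50% | 19-50% |

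The loss falls to one half at a baseline incidence of 50% (OR 1), 35-45% (OR 3) or 26-42% (OR 10). Outside these inputs it can be smaller: with pb = 20%, pf = 30% and every baseline-episode patient having a later one, it is 1 − 0.20/0.30 = 33%.

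**Cross-checks.** A simulation with patient-level frailty gave losses of 84-89% at about 9% baseline incidence, 67-76% at about 18-20%, 49-61% at about 29-34%, and 31-42% at about 42-50%. In a simulated 200-patient data set with 20% assumed baseline incidence, a complete-case linear fit used 26 of the 120 patients who had an outcome.

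**Consequence for precision.** Take 100 patients per arm (the completer number in Protocol section 9.2), 60 of them with an on-treatment episode, an assumed 0.5 SD difference and 2-sided alpha 0.1. With all 60 per arm, power is 86%. With 30 per arm (pb = 40%, OR 3) it is 62%, and with 12 per arm (pb = 20%, OR 1) it is 34%.

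**The case against.** Five points can be made on the other side.

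1. **No document gives the baseline incidence.** The statement about non-secretagogues concerns clinical risk, and the remark on sparse data in SAP Appendix 1 concerns patient-reported events, not sensor readings. This stands. A reader might infer it is established that most patients with on-treatment episodes are lost; it is only probable.

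2. **On-treatment durations are still reported.** SAP section 5.11.1 requires summary statistics by visit and treatment for all continuous measures, and section 5.11.2 adds the raw mean. These do not need a baseline episode. This stands: only the model-based comparison is affected.

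3. **A programmer could enter 0 for the missing baseline.** Done for the covariate alone, this loses nobody and leaves the outcome unchanged, although the covariate then mixes having no episode with length of episode. Entering 0 for the outcome as well would turn duration into a blend of incidence and length. The SAP does not say which applies, so the point shows that the omission can be avoided, not that the text avoids it.

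4. **The link between variable and model is inferred.** Section 5.11.2.1 lists individual durations, the average appears in section 5.11.3.2, and section 5.11.3 says it also holds variables for possible exploratory use. This changes little: a patient without a baseline episode has neither an individual nor an average baseline duration.

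5. **The variable is exploratory and other measures cover hypoglycemia.** Percent and minutes per day below range are 0, not undefined, without hypoglycemia, and the rate model needs no baseline episode. This stands and limits the weight of the point.

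**Conclusion.** Applied as written, with the undefined value left missing, the rule in SAP section 5.11.2 removes every patient without a baseline episode from the modelled comparison of episode duration. That follows from the text. These are probably most of the patients who have an episode on treatment: about 60-95% if 5-20% have a baseline episode, given on-treatment incidence of 40-80% and an odds ratio of 1-10. The incidences and odds ratios are all assumptions, and the loss can fall below half at higher baseline incidence.

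A reader might go further and infer that the trial cannot show whether the weekly insulin prolongs hypoglycemia, or that on-treatment episodes vanish from the report. The documents do not support that: the raw by-arm durations, time below range and episode rates all remain. The defect is confined to one exploratory model, but it touches the duration concern that the protocol itself raises and is cheap to repair.

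**What to change.** In SAP section 5.11.2, exempt episode duration from the rule on the baseline value of the dependent variable. Use instead a baseline covariate that every patient in the FGM set has: baseline percent time <70 mg/dL, already derived under section 5.11.2.1, or baseline HbA1c, as in the SAP's own episode-rate model. State also that:

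- the outcome is not set to 0 at a visit without an episode;
- the numbers of patients and episodes per arm are reported beside the estimate;
- the estimate is labelled as conditional on having an on-treatment episode, with percent time <70 and <54 mg/dL as the unconditional comparison.

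An episode-level mixed model on log minutes is an option, not a requirement. The same edit could reconcile the upper episode threshold, which is <70 mg/dL in section 5.11.2.1 and ≤70 mg/dL in section 5.11.3.2.

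The cost is one SAP paragraph and no new data. The change restores every FGM-set patient with a post-baseline episode. It does not make the comparison fully randomized: it still selects on a post-randomization event, so it can be confounded if the arms differ in who has episodes.
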